Table 2-2: On Study Assessments Treatment Phase - Arm A - Nivolumab in Combination with Ipilimumab (CA209848)

Procedure	Day 1	Every 2 weeks (i.e., every subsequent cycle Day 1) (± 3 Days)	Every 6 weeks (i.e. every 3 cycles Day 1 (± 3 Days))	Every 12 weeks (i.e. every 6 cycles Day 1) (± 7 Days)	Notes For the purposes of this table, a cycle refers to nivolumab every 2 weeks
Vital signs	X	X			Temperature, blood pressure, and heart rate. Must be performed prior to dosing.
Concomitant medication	Continuously				
Adverse events (including serious and non-serious) assessment	Continuously				Record at each visit. All AEs (SAEs or non-serious AEs), including those associated with SARS-CoV-2 infection, must be collected continuously throughout the treatment period. Adverse events and laboratory values will be graded according to the NCI-CTCAE version 5.
Laboratory Assessments					
Hematology and chemistry	X	X			See Section 9.4.3 Clinical Safety Laboratory Assessments. Must be performed within 72h prior to dosing.
Thyroid function testing	X		X (see note)		Thyroid function testing should be done every 4 weeks (i.e., Day 1 of every other cycle) for the first 10 cycles, and then every 8 weeks until completion of study treatment. Must be performed within 72h prior to dosing.
Pharmacokinetic Assessment	See Section 9.5				
Immunogenicity Assessment	See Section 9.5				
Biomarker assessment	See Section 9.8				
Collection of tumor tissue for biomarkers upon disease progression	See Section 9.8				If a biopsy has been performed and tissue is available, participants are requested to submit fresh tumor tissue for biomarker

Table 2-2: On Study Assessments Treatment Phase - Arm A - Nivolumab in Combination with Ipilimumab (CA209848)

Procedure	Day 1	Every 2 weeks (i.e., every subsequent cycle Day 1) (± 3 Days)	Every 6 weeks (i.e. every 3 cycles Day 1 (± 3 Days)	Every 12 weeks (i.e. every 6 cycles Day 1) (± 7 Days)	Notes For the purposes of this table, a cycle refers to nivolumab every 2 weeks
					research. Tissue submission is optional and biopsy is not required by protocol.
Additional research collection	See Section 9.8.1				
Efficacy Assessments					
Body Imaging				X (see note)	For Solid Tumors: Tumor Assessments should occur every 12 weeks (± 7 days) until BICR confirmation of disease progression or treatment discontinuation(including treatment beyond progression), whichever comes later. See Section 9.1.1 for further details.

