Procedure	Day 1	Every 4 weeks (i.e. each subsequent cycle Day 1) (± 3 Days)	Every 12 weeks (i.e. every 3 cycles Day 1) (± 7 Days)	Notes For the purposes of this table, a cycle refers to nivolumab every 4 weeks
Safety Assessments				
Pregnancy test	X	X		WOCBP only: Serum or urine pregnancy test (minimum sensitivity 25 IU/L or equivalent units of HCG) to be done within 24h prior to first dose of study treatment, and then every 4 weeks (± 1 week) regardless of dosing schedule.
Weight	X	X		Weight must be assessed within 72h prior to dosing
Physical examination and ECOG, Karnofsky or Lansky Performance Status	X			Within 72 hours prior to dosing. See Appendix 6 for ECOG performance status (for participants ≥ 16 years old with solid tumors), and Appendix 9 for Karnofsky (participants ≥ 16 years old with CNS as primary tumor) and Lansky (for all participants < 16 years old)
Targeted physical examination and ECOG, Karnofsky or Lansky Performance Status		X		Targeted examination must be performed within 72 hours prior to dosing and include at a minimum the cardiovascular, gastrointestinal, and pulmonary body systems. See Appendix 6 for ECOG performance status (for participants ≥ 16 years old with solid tumors), and Appendix 9 for Karnofsky (participants ≥ 16 years old with CNS as primary tumor) and Lansky (for all participants < 16 years old)
Vital signs	X	X		Temperature, blood pressure, and heart rate. Must be performed prior to study drug administration.
Concomitant medication	Continuously			
Adverse events (including serious and non-serious) assessment	Continuously			Record at each visit. All AEs (SAEs or non-serious AEs), including those associated with SARS-CoV-2 infection, must be collected continuously throughout the treatment period. Adverse events and laboratory values will be graded according to the NCI-CTCAE version 5.

Table 2-3: On Study Assessments Treatment Phase - Arm B - Nivolumab Monotherapy (CA209848)

Procedure	Day 1	Every 4 weeks (i.e. each subsequent cycle Day 1) (± 3 Days)	Every 12 weeks (i.e. every 3 cycles Day 1) (± 7 Days)	Notes For the purposes of this table, a cycle refers to nivolumab every 4 weeks
Laboratory Assessments				
Hematology and chemistry	X	X		See Section 9.4.3 Clinical Safety Laboratory Assessments. Must be performed within 72h prior to study drug administration.

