Procedure	Day 1	Every 2 weeks (i.e. every subsequent cycle Day 1) (± 3 Days)	Every 6 weeks (i.e. every 3 cycles Day 1 (± 3 Days))	Every 12 weeks (i.e. every 6 cycles Day 1) (± 7 Days)	Notes For the purposes of this table, a cycle refers to nivolumab every 2 weeks
Vital signs	X	X			Temperature, blood pressure, and heart rate. Must be performed prior to dosing.
Concomitant medication	Continuously				
Adverse events (including serious and non-serious) assessment	Continuously				Record at each visit. All AEs (SAEs or non-serious AEs), including those associated with SARS-CoV-2 infection, must be collected continuously throughout the treatment period. Adverse events and laboratory values will be graded according to the NCI-CTCAE version 5.
Laboratory Assessments					
Hematology and chemistry	X	X			See Section 9.4.3 Clinical Safety Laboratory Assessments. Must be performed within 72h prior to dosing.
Thyroid function testing	X		X (see note)		Thyroid function testing should be done every 4 weeks (i.e., Day 1 of every other cycle) for the first 10 cycles, and then every 8 weeks until completion of study treatment. Must be performed within 72h prior to dosing.
Pharmacokinetic Assessment	See Section 9.5				
Immunogenicity Assessment	See Section 9.5				
Biomarker assessment	See Section 9.8				
Collection of tumor tissue for biomarkers upon disease progression	See Section 9.8				If a biopsy has been performed and tissue is available, participants are requested to submit fresh tumor tissue for biomarker

Table 2-4: On Study Assessments Treatment Phase – Arm B Rollover – Participants Treated with Nivolumab in Combination with Ipilimumab After Disease Progression During Nivolumab Monotherapy (CA209848)

Procedure	Day 1	Every 2 weeks (i.e. every subsequent cycle Day 1) (± 3 Days)	Every 6 weeks (i.e. every 3 cycles Day 1 (± 3 Days))	Every 12 weeks (i.e. every 6 cycles Day 1) (± 7 Days)	Notes For the purposes of this table, a cycle refers to nivolumab every 2 weeks
					research. Tissue submission is optional and biopsy is not required by protocol.
Additional research collection	See Section 9.8.1				
Efficacy Assessments					
Body Imaging				X (see note)	For Solid Tumors: Tumor Assessments should occur every 12 weeks (± 7 days) until BICR confirmation of disease progression or treatment discontinuation (including treatment beyond progression), whichever comes later. See Section 9.1.1 for further details.

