Seventy-six (76) participants in the salvage setting are required for each of tTMB and bTMB for nivolumab in combination with ipilimumab arm. Based on the currently observed approximate 40% concordance between tTMB-H and bTMB-H in this study, the total sample size for nivolumab in combination with ipilimumab arm will be approximately 122. Nivolumab monotherapy arm is a non-comparative arm to evaluate the contribution of components. Approximately 183 to 342 participants will be randomized into nivolumab in combination with ipilimumab (n=122) and nivolumab monotherapy (n=61) in a 2:1 randomization ratio. Moreover, if concordance rate between tTMB-H and bTMB-H is x%, sample size for nivolumab in combination with ipilimumab arm will be approximately $76+76-76*x\%$ and total sample size will be approximately $1.5*(76+76-76*x\%)$. For example, if x=30% the total sample size will be 194 and if x is close to 0% the total sample size will be 228. Note the sample sizes(s) for the primary endpoint of ORR in each of tTMB-H and bTMB-H in nivolumab + ipilimumab arm remains 76 regardless of the concordance but the final sample size required for the study may change depending on the observed concordance rate and depending on whether or not the bTMB cut-off is increased after the first interim analysis (see [Section 10.3.6](#)).

Should the tTMB-H population reach approximately 76 before the bTMB-H population, then enrollment will continue only with participants required to meet the eligibility criteria for bTMB until approximately 76 participants is reached in the bTMB-H population. Should the bTMB-H population reach approximately 76 before the tTMB-H population then enrollment will continue only with participants required to meet the eligibility requirement for tTMB-H until approximately 76 participants is reached in the tTMB-H population.

All tumor types will be pooled in the analysis. In order to ensure that 1 tumor type does not unduly impact the overall pooled final efficacy analysis, a cap of approximately 15% of participants per tumor type will be enforced.

The final analysis of the primary endpoint ORR based on BICR assessments for tTMB high population will be performed at least 12 months after all tTMB \geq 10 mut/Mb participants in the salvage setting have been randomized and study randomization is completed. Final analysis of the primary endpoint ORR based on BICR assessments for bTMB high population will be performed

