10.3.2 Safety Analyses

Endpoint Definition	Statistical Analysis Methods

Primary
	
Not applicable

Endpoint Definition	Statistical Analysis Methods
Secondary	
Safety and tolerability	
Descriptive statistics of safety will be presented using the National Cancer Institute (NCI) Common Terminology Criteria for Adverse Events (CTCAE) version 5.0 by tumor types. All on-study AEs and SAEs and drug-related AEs and SAEs will be tabulated using worst grade per NCI CTCAE version 5.0 criteria by system organ class and MedDRA preferred term.
 
On-study lab parameters including hematology, coagulation, chemistry, liver function and renal function will be summarized using worse grade per NCI CTCAE version 5.0 criteria.

Exploratory	Will be described in the statistical analysis plan finalized before database lock

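### By-arm worst-grade lab tables mix unequal draw frequency with post-rollover combination exposure that would count under monotherapy; cut Arm B at rollover and show a common-visit sensitivity table

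*Combined protocol and SAP*

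**What the plan says.** Section 10.3.2 gives one sentence on laboratory safety: "On-study lab parameters including hematology, coagulation, chemistry, liver function and renal function will be summarized using worse grade", by CTCAE version 5.0. It is read here as worst grade, the term used for adverse events just before it. The section presents safety descriptively and by tumor type. It does not define which draws count as on-study, limit them to common visits, or say where labs taken after rollover belong. Section 10.3 sets the default grouping as the arm to which the participant was randomized.

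The schedules in Section 2 tie hematology and chemistry to dosing:

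- **Arm A (Table 2-2):** Day 1, then "Every 2 weeks (i.e., every subsequent cycle Day 1) (± 3 Days"), with the note "See Section 9.4.3 Clinical Safety Laboratory Assessments. Must be performed within 72h prior to dosing".
- **Arm B (Table 2-3):** Day 1, then "Every 4 weeks (i.e. each subsequent cycle Day 1) (± 3 Days"), with the note "See Section 9.4.3 Clinical Safety Laboratory Assessments. Must be performed within 72h prior to study drug administration".
- **Arm B rollover (Table 2-4):** Day 1, then "Every 2 weeks (i.e. every subsequent cycle Day 1) (± 3 Days").

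Thyroid tests are handled differently. In Arm A, "Thyroid function testing should be done every 4 weeks (i.e., Day 1 of every other cycle) for the first 10 cycles"; in Arm B they are also 4-weekly at first, and both arms then move to 8-weekly. Table 2-5 adds follow-up draws at about Day 30 and Day 100 after the last dose for everyone.

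Section 10.1 says: "Nivolumab monotherapy arm is a non-comparative arm to evaluate the contribution of components". Section 10.3.4 repeats the patient-reported outcome analyses for participants who receive the combination after progressing on monotherapy. Section 10.3.2 has no matching provision for labs.

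**The concern.** A worst grade is a maximum over draws. For the same clinical course, a denser set of draws cannot give a lower maximum, and it gives a higher one whenever a value fluctuates or resolves between the sparser draws. The by-arm tables therefore partly measure how often blood was taken.

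Rollover adds a second effect in the same table. With grouping by randomized arm and no cut, an Arm B participant who rolls over contributes 2-weekly draws on nivolumab plus ipilimumab to the monotherapy column.

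What is at stake is the reading of what ipilimumab adds to laboratory toxicity. Safety is a secondary objective, and Section 3.3.1 already describes the two regimens as having comparable safety. A reader will look to these tables for support or contradiction.

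**Working it through.** The plan states no figure on this point, so there is none to reproduce. Draw frequencies come from Tables 2-2 to 2-5. Abnormality rates and episode durations are **assumptions**; the documents give neither.

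**1. Scheduled draws.** Number of draws = weeks / interval + 1.

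| Weeks on treatment | Arm A | Arm B, no rollover |
|---|---|---|
| 12 | 12/2 + 1 = 7 | 12/4 + 1 = 4 |
| 24 | 24/2 + 1 = 13 | 24/4 + 1 = 7 |
| 104 | 104/2 + 1 = 53 | 104/4 + 1 = 27 |

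The Day 1 draw precedes the first dose, so post-baseline counts at 24 weeks are 12 and 6. The two follow-up draws add 2 to each arm.

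**2. Chance that a scheduled draw catches one episode (random onset).** For a fixed duration of d days this is min(1, d/14) in Arm A and min(1, d/28) in Arm B:

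- 7 days: 50% v 25%
- 14 days: 100% v 50%
- 21 days: 100% v 75%
- 28 days or more: 100% v 100%

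For exponential durations with mean d and draw interval t, the chance is (d/t)(1 − exp(−t/d)):

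| Mean d (days) | t = 14 (Arm A) | t = 28 (Arm B) | Ratio |
|---|---|---|---|
| 7 | 0.43 | 0.25 | 1.76 |
| 14 | 0.63 | 0.43 | 1.46 |
| 28 | 0.79 | 0.63 | 1.24 |
| 56 | 0.89 | 0.79 | 1.12 |

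**3. Recorded peak grade.** A longer episode that is caught in both arms can still be graded lower in Arm B if its grade changes. Take a value that rises and falls linearly over 42 days, just short of 5 at its peak and graded by rounding down. It is at grade 3 or higher for 0.4 × 42 = 16.8 days. Arm A always has a draw in that window. Arm B has one with probability 16.8/28 = 60%.

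**4. Recorded rate at equal true toxicity, 24 weeks.** With independent draws at 1% each, 1 − 0.99^13 = 12.2% in Arm A and 1 − 0.99^7 = 6.8% in Arm B. Post-baseline only, 1 − 0.99^12 = 11.4% and 1 − 0.99^6 = 5.9%. Independence is close to the worst case. In a simulated autocorrelated lab value with 1% exceedance at any one time, the rates (Day 1 included) are 11.8% v 6.4% at a 7-day correlation time and 5.9% v 4.6% at 90 days.

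**5. Rollover.** As an illustration, suppose an Arm B participant rolls over at week 12 and is followed to week 24. Draws fall at weeks 0, 4, 8 and 12 (4), then at weeks 14 to 24 every 2 weeks (6). That makes 10, against 7 without rollover and 13 in Arm A. The last 6 are taken on the combination.

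**6. Net direction.** Two limiting cases, with ipilimumab assumed to add some lab toxicity:

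- Short-lived abnormalities and few rollovers: only the draw-frequency effect operates, and the contrast between arms is overstated.
- Stable abnormalities of 28 days or more and many rollovers: there is no detection gap, combination toxicity is counted under Arm B, and the contrast is understated.

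The documents do not say which case is nearer, because they give neither the rollover frequency nor the abnormality durations.

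**7. After the fix.** At post-baseline visits common to both arms there are 6 draws each over 24 weeks. At an independent 1% per draw, both arms expect 1 − 0.99^6 = 5.9%, provided findings at the omitted Arm A visits do not change the later values.

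**The case against.** A reader might infer that the combination must look more toxic than monotherapy by construction, with the direction of error fixed. The documents do not support this. It holds for pre-rollover data and short-lived abnormalities, but no rule cuts labs at rollover, and post-rollover labs push Arm B upward (step 6).

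Other points on the other side, and what stands of each:

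- **No between-arm lab comparison is planned.** Safety is descriptive, there is no safety test or decision rule, and Arm B is labelled non-comparative. The phrase about contribution of components is in the sample-size section, so extending it to labs is an inference. This stands, and it limits the consequence to interpretation. By-arm tables will still be produced under Section 10.3.
- **The SAP may settle it.** Section 10.3 says a SAP will be finalized before database lock. No separate SAP text on labs was available, so a rule may exist there. Section 10.3.2 itself explicitly defers only exploratory safety analyses to it.
- **Worst grade is conventional, and pre-dose labs naturally follow dosing.** This stands. The all-draw table shows each participant's peak recorded toxicity and should remain the main display.
- **The larger figures rest on assumed independent draws.** This stands. They are illustrations, and persistent abnormalities shrink them.
- **A common-visit table has its own bias.** A grade found at an intermediate Arm A visit can trigger delay and at least weekly re-evaluation under Section 7.4.1, and may have fallen by the next common visit. That would understate Arm A. This stands, so such a table can only be a sensitivity display.

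**Conclusion.** The concern holds in a limited form. The by-arm worst-grade lab tables combine two effects that the plan does not separate: roughly twice as many scheduled draws in Arm A before rollover, and combination-era labs counted under Arm B after it.

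The first effect favors recording short-lived abnormalities in Arm A. Under the exponential illustration the detection ratio runs from about 1.8 (mean 7 days) to 1.1 (mean 56 days), and there is no detection gap for stable abnormalities of 28 days or more. Unscheduled tests would narrow the gap further. The second effect works the other way and cannot be sized from the documents. A statement that combination toxicity is overstated overall would go too far.

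No error rate or efficacy conclusion is affected, and thyroid tests are not affected before rollover because both arms follow the same calendar. The conclusion assumes that the SAP adds no rule on lab windows or rollover.

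**What to change.** In Section 10.3.2, or in the SAP before database lock:

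1. For by-arm lab tables, cut Arm B at the first dose of the combination and tabulate post-rollover labs separately, in line with Section 10.3.4.
2. Keep the all-draw worst-grade table as the main safety display. Show the scheduled draw frequency and the number of draws per arm beside it.
3. Add a labelled sensitivity table of worst post-baseline grade at 4-weekly visits common to both arms. In Arm A these are cycles 3, 5, 7 and so on. Assign visits by calendar window, because doses are delayed and not skipped (Section 7.4), so cycle numbers drift. Leave out the Day 1 pre-dose draw.

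The cost is some extra tables from data already collected, with no change to any visit or clinical procedure. The drawback is that the sensitivity table discards about half the Arm A draws and may miss Arm A peaks managed between common visits. It supplements the all-draw table and does not replace it.

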10.3.3 Pharmacokinetics Analysis

The nivolumab and ipilimumab concentration data obtained in this study may be combined with data from other studies in the clinical development program to develop population PK models. These models may be used to evaluate the effects of intrinsic and extrinsic covariates on the PK of nivolumab and to determine measures of individual exposure (such as steady state peak, trough and time averaged concentration). Model determined exposures may be used for exposure response analyses of selected efficacy and safety endpoints. If the analyses are conducted, the results of population PK and exposure response analyses will be reported separately.

10.3.4 Outcomes Research Analyses

The analysis of EQ-5D-3L and EORTC QLQ-C30 data will be performed in all treated participants who have an assessment at baseline and at least 1 subsequent assessment while on treatment. Questionnaire completion rate, defined as the proportion of questionnaires received out of the expected number, will be calculated and summarized at each assessment point. Analyses of PROs will be replicated for subjects that are treated with nivolumab combined with ipilimumab after disease progression under nivolumab monotherapy.

EQ-5D data will be described by treatment group in the following ways:

- EQ-5D index scores and post-baseline changes in scores will be summarized at each assessment time point using descriptive statistics (ie, N, mean with SD and 95% CI, median, first and third quartiles, minimum, maximum).
- EQ-VAS scores and post-baseline changes in scores will be summarized at each assessment time point using descriptive statistics (ie, N, mean with SD and 95% CI, median, first and third quartiles, minimum, maximum).
- The proportion (N) of participants reporting no, moderate, or extreme problems will be presented for each of the 5 EQ-5D dimensions at each assessment time point. Participants with missing data will be excluded from the analysis.
- A by- participant listing of the level of problems in each dimension, corresponding EQ-5D health state (ie, 5-digit vector), EQ-5D index score, and EQ-VAS score will be provided.

EORTC QLQ-C30 data will be described by treatment group in the following ways:

- Scale and item scores will be summarized at each assessment time point using descriptive statistics (ie, N, mean with SD and 95% CI, median, first and third quartiles, minimum, maximum).
- Changes from baseline in scale and item scores will be summarized at each post-baseline assessment time point using descriptive statistics (ie, N, mean with SD and 95% CI, median, first and third quartiles, minimum, maximum).

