Brain Imaging	X (See note)	X (See note)	Primary CNS neoplasms: MRI without and with contrast should have MRI of the brain approximately every 12 weeks (± 7 days) until BICR confirmation of disease progression or treatment discontinuation (including treatment beyond progression), whichever comes later. For Solid Tumors: Participants with a history of brain metastasis or symptoms should have a surveillance brain MRI per standard of care (approximately 12 weeks) or sooner if clinically indicated. See Section 9.1 for further details.
Other: Bone Scan	X (See note)	X (See note)	As clinically indicated per local standards. See Section 9.1 for further details.
Participant status		X	Every 3 months after X02; may be accomplished by visit or phone contact, to update survival information Collect all subsequent anti-cancer treatment.

^a Participants must be followed for at least 100 days after last dose of study treatment. Follow-up visit #1 (FU1) occurs approximately 30 days (± 7 days) after the last dose or coinciding with the date of discontinuation (± 7 days) if date of discontinuation is greater than 30 days after last dose. Follow-up visit #2 (FU2) occurs approximately 100 days (± 7 days) from last dose. Both FU1 and FU2 should be conducted in person.

- ^b Survival Follow-up visits to occur every 3 months \pm 14 days from Follow-up Visit 2. BMS may request that survival data be collected on all treated participants outside of the protocol window. At the time of this request, each participant will be contacted to determine their survival status unless the participant has withdrawn consent for all contacts. Survival follow-up may be conducted in person or by telephone.

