9.10 Patient-Reported Outcomes

Participants, ≥ 18 years of age at baseline, will be asked to complete the 30-item European Organization for Research and Treatment of Cancer Quality of Life Questionnaire (EORTC QLQ-C30) and 3-level version of the EuroQol Group's EQ-5D (EQ-5D-3L) after randomization but prior to first dose, at on-study clinic visits planned to occur every 4 weeks (nivolumab arm) or 6 weeks (nivolumab plus ipilimumab arm) while on treatment, and at follow-up visits 1 and 2. In addition, the EQ-5D-3L will be completed at designated time points during the survival follow-up phase. In cases where a dose of treatment drug is delayed, the PRO assessment should also be delayed.

The EORTC QLQ-C30 will be used to assess the effects of disease symptoms on functioning and well-being. The QLQ-C30⁵⁵ is the most commonly used quality of life instrument in oncology trials. The instrument's 30 items are divided among five functional scales (physical, role, cognitive, emotional, and social), nine symptom scales (fatigue, pain, nausea/vomiting, dyspnea, insomnia, appetite loss, constipation, diarrhea, and financial difficulties), and a global health/quality of life scale. With the exception of two items included in the global health/quality of life scale, for which responses range from 1 (Very poor) to 7 (Excellent), item responses range from 1 (Not at all) to 4 (Very much). Raw scores for the QLQ-C30 are transformed to a 0-100 metric such that higher values indicate better functioning or quality of life or a higher level of symptoms. The questionnaire uses a 1-week recall period.

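### The PRO analysis set requires a form completed on treatment, so follow-up forms from participants who stop before their first on-treatment form enter no score summary

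*Combined protocol and SAP*

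**What the plan says.** Section 10.3.4 states that analysis of both questionnaires will be "performed in all treated participants who have an assessment at baseline and at least 1 subsequent assessment while on treatment". Within that set, scores and changes from baseline are summarised descriptively, by treatment group, at each assessment time point.

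Section 9.10 places the forms after randomization but before the first dose, then "at on-study clinic visits planned to occur every 4 weeks (nivolumab arm) or 6 weeks (nivolumab plus ipilimumab arm) while on treatment". Both questionnaires are due again at FU1 and FU2. For the period after that, "the EQ-5D-3L will be completed at designated time points during the survival follow-up phase". Tables 2-2 and 2-3 give the same 6-week and 4-week schedules, and Table 2-5 confirms the follow-up collection. On timing, its footnote says "Follow-up visit #1 (FU1) occurs approximately 30 days (± 7 days) after the last dose" and "Follow-up visit #2 (FU2) occurs approximately 100 days (± 7 days) from last dose".

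Forms are requested only from participants aged 18 or over at baseline. If a dose is delayed, the form is delayed with it.

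**The concern.** Collection and analysis do not match. The protocol asks early stoppers for questionnaires after treatment, then defines an analysis set that they cannot enter. Their FU1 and FU2 forms, and any later EQ-5D-3L forms, appear in no score summary. Their baseline forms drop out as well.

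The remaining FU1/FU2 and survival follow-up summaries describe only people who stayed on treatment long enough to complete an on-treatment form. If the earliest stoppers feel worse than average, which is plausible but not documented here, those summaries will look somewhat better than the experience of all treated adults who returned forms. The qualifying visit also falls two weeks later in the combination arm, so the selection is not the same in the two columns of a table.

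**Working it through.** **Plan's own figure.** There is none to reproduce: the documents state no sample size, power or expected attrition for the PRO analysis. The check compares the sections and adds one illustration.

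**Step 1: does the on-treatment condition exclude FU1 and FU2?** Section 9.10 lists on-treatment visits and follow-up visits as separate items: "every 4 weeks (nivolumab arm) or 6 weeks (nivolumab plus ipilimumab arm) while on treatment, and at follow-up visits 1 and 2". Read consistently, a form at FU1 or FU2 does not satisfy Section 10.3.4, and no other text in the documents restores these forms.

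**Step 2: who is excluded by this condition?** A treated adult with a baseline form who completes no on-treatment form afterwards.

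- Combination: nivolumab is given at weeks 0, 2 and 4 before the first on-treatment form at week 6. A participant can receive three nivolumab doses and still be excluded.
- Monotherapy: nivolumab is given at week 0, and the first on-treatment form is due at week 4. Exclusion follows stopping after one dose.
- These are the earliest nominal times, since a dose delay moves the form later.

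**Step 3: when would the unused forms be collected?** FU1 is about 30/7 = 4.3 weeks and FU2 about 100/7 = 14.3 weeks after the last dose.

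| Last dose | Arm | FU1 (week) | FU2 (week) |
|---|---|---|---|
| Week 0 | either | 4.3 | 14.3 |
| Week 2 | combination | 6.3 | 16.3 |
| Week 4 | combination | 8.3 | 18.3 |

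**Step 4: which summaries change?** Summaries are made visit by visit. Excluded participants have no on-treatment post-baseline form, so on-treatment means are identical with or without them. Participants who stop after one on-treatment form are in the set and keep their FU1/FU2 forms. The summaries that can change are baseline, FU1, FU2 and EQ-5D-3L in survival follow-up.

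**Step 5: illustrative size.** Assume a constant hazard of stopping, equal in both arms, with a proportion p off treatment by week 12. The proportion off treatment by week t is 1 − (1 − p)^(t/12). This is 1 − (1 − p)^(1/2) at week 6 and 1 − (1 − p)^(1/3) at week 4.

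| p (assumed) | Combination, week 6 | Monotherapy, week 4 | Ratio |
|---|---|---|---|
| 10% | 5.1% | 3.5% | 1.49 |
| 20% | 10.6% | 7.2% | 1.47 |
| 30% | 16.3% | 11.2% | 1.46 |
| 40% | 22.5% | 15.7% | 1.44 |

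With equal hazards, the schedule alone makes the excluded share about 1.4 to 1.5 times as large in the combination arm. These shares are upper limits on what a wider set would regain, because they include people who die or never return a follow-up form.

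**The case against.** The strongest reply is that little rests on these data. Section 4 lists the PRO objectives as exploratory, Section 10.3.4 plans only descriptive summaries, and Section 10.1 calls the monotherapy arm non-comparative. Describing PROs in people with on-treatment exposure is a defensible choice. Section 10.3 leaves participant selection and missing data to a separate SAP, which could define the on-treatment period or add a sensitivity analysis. All of this stands, and it limits the importance of the point. It does not remove the mismatch in the text available.

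A constant hazard may also overstate early stopping. The first scheduled tumour assessment is at week 12 in both arms, and treatment beyond progression is allowed. Forms are completed at the start of the visit, before dosing, so someone stopped at the week 4 or week 6 visit may already have one. This too stands: the table in the working is an illustration, not a forecast.

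Three stronger readings are tempting, and the documents do not support them.

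- A reader might infer that more toxicity-related stopping in the combination arm widens the gap. Section 3.2.3 does report more Grade 3/4 events with the same combination schedule than with monotherapy in the NSCLC phase 1b study (33% versus 19%). It also reports that treatment-related Grade 3-4 events led to discontinuation in 8%, similar to monotherapy. Section 3.3.1 describes the safety profiles at the selected dose as comparable. Only the two-week schedule difference is established.
- A reader might infer that the completion rate is inflated. Section 10.3.4 defines it as "Questionnaire completion rate, defined as the proportion of questionnaires received out of the expected number" and does not say which population supplies the expected number. The population is unstated, which does not show that it is wrong.
- A reader might apply the illustrative shares to the planned 122 and 61 participants and report a headcount. Those are randomized numbers, the shares are assumed, and some of the people counted would have no follow-up form to regain.

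**Conclusion.** The point holds in a narrow form. As written, Section 10.3.4 discards follow-up questionnaires that the protocol collects from participants who stop before a first on-treatment form, and the nominal hurdle is week 6 in the combination arm against week 4 in the monotherapy arm. The selection affects the baseline, FU1/FU2 and survival follow-up summaries and leaves on-treatment means untouched.

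Its size cannot be computed from the documents. The illustrative range, 5.1% to 22.5% against 3.5% to 15.7%, rests on an assumed equal constant hazard and an assumed 10% to 40% off treatment by week 12. That range counts early stoppers, of whom only those returning a follow-up form would be regained. Any favourable shift in follow-up means further assumes that early stoppers report worse scores. This is a minor, inexpensive improvement to an exploratory analysis and has no bearing on the primary endpoint.

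**What to change.** In Section 10.3.4, delete the words restricting the qualifying later form to the treatment period. The set then becomes all treated adults with a baseline form and at least one post-baseline form of any kind: on-treatment, FU1, FU2 or, for EQ-5D-3L, survival follow-up. Carry the same definition into the SAP.

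The cost is one phrase, with no new data, visits or participants. Follow-up means may look slightly less favourable. The 4-week and 6-week collection schedules stay as they are. The difference between them would no longer decide membership for early stoppers who return a follow-up form.
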